8.2.2. End-of-Treatment Visit

An End-of-Treatment visit should occur 30 days (\pm 7 days) from the last dose of study drug or prior to the start of a new cGVHD treatment. If the subject starts a new cGVHD treatment less than 7 days after the Progressive Disease visit, only those procedures not conducted at the Progressive Disease visit should be performed at the End-of-Treatment visit.

The following procedures will be performed at the End-of-Treatment visit:

- Complete physical examination
- Vital signs and performance status (KPS)
- Hematology

- Serum chemistry
- Donor/host chimerism testing Lee cGVHD Symptom Scale ([Appendix E](#))
- cGVHD NIH Form assessment ([Appendix F](#) and [Appendix G](#))
- Photographic imaging of cGVHD
- Immunosuppressant level – if applicable
- Quantitative serum immunoglobulins (IgA, IgG, and IgM)
- Review returned subject dosing diary
- Review adverse events and concomitant medications (including corticosteroid requirements and any new cGVHD treatment if applicable)
- Final drug accountability
- Biomarker sampling

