8.3.1. Response Follow-up

Subjects who discontinue the study for reasons other than progressive disease will be followed every 12 weeks (± 7 days) by clinic visit until progressive disease. During this period, the following procedures will be performed:

- Symptom-directed physical examination
- Vital signs and performance status (KPS)
- Hematology
- Serum chemistry
- Donor/host chimerism testing cGVHD NIH Form assessment ([Appendix F](#) and [Appendix G](#))
- Lee cGVHD Symptom Scale ([Appendix E](#))
- Photographic imaging of cGVHD
- Review corticosteroid requirements and any new cGVHD treatment if applicable

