9.2. Withdrawal from Study Treatment

Study treatment will be discontinued in the event of any of the following events:

- cGVHD progression (see definition in [Section 7.2.1](#))
- Unacceptable toxicity: an intercurrent illness or AE that prevents further ibrutinib administration.
- Noncompliance with study medication.
- Investigator's decision (such as chronic noncompliance, significant protocol deviation, or best interest of the subject)
- Withdrawal of consent for treatment by subject
- Malignancy progression/relapse.
- Subject's condition no longer requires study treatment.
- Subject becomes pregnant
- Study termination by Sponsor
- Death

All subjects, regardless of reason for discontinuation of study treatment will undergo an End-of-Treatment Visit and be followed for progression and survival.

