10.5. Safety Analysis

The safety variables to be analyzed include adverse events, clinical laboratory test results (hematology and chemistry), and other safety measurements. They will be summarized by descriptive statistics. No formal statistical testing is planned.

Exposure to ibrutinib first dose and reasons for discontinuation from study treatment will be tabulated.

Adverse Events

Adverse event parameters to be evaluated are the type, incidence, and intensity of adverse events; the relationship of adverse events to ibrutinib; and the action taken with respect to ibrutinib treatment due to adverse events.

The verbatim terms used in the eCRF will be coded using the Medical Dictionary for Regulatory Activities (MedDRA).

Treatment-emergent adverse events are those adverse events occurring after the first dose of study drugs and within 30 days following the last dose of study drug; any adverse event that is considered study drug-related regardless of the start date of the event; or any adverse event that is present at baseline but worsens after the first administration of study drug in severity or is subsequently considered drug-related by the Investigator. All treatment-emergent adverse events will be included in the analysis.

For each adverse event, the percentage of subjects who experience at least 1 occurrence of the given event will be summarized. The number and percent of subjects with treatment-emergent adverse events will be summarized according to intensity (NCI CTCAE v. 4.03) and drug relationship as well as categorized by system organ class and preferred term. Summaries, listings, datasets, or subject narratives may be provided, as appropriate, for those subjects who die, who discontinue treatment due to an adverse event, or who experience a severe or a serious adverse event.

Clinical Laboratory Tests

All laboratory values will be converted to standard international units and will be graded using the [NCI CTCAE v. 4.03](#).

A summary of the shifts in selected laboratory hematology and serum chemistry parameters from baseline to the worst toxicity grade during the study will be tabulated.

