3.1.3 Postbaseline Value

The postbaseline value is defined as a measurement taken after the first dose of study drug.

For subjects with a valid, nonzero baseline value:

$$\text{Change from baseline} = \text{postbaseline value} - \text{baseline value};$$

$$\% \text{ change from baseline} = (\text{change from baseline}/\text{baseline}) * 100.$$

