6.1 Adverse Events

The verbatim terms used in the CRF by investigators to identify adverse events (AEs) will be coded using the Medical Dictionary for Regulatory Activities (MedDRA). Adverse events will be graded by the investigator according the National Cancer Institute common terminology criteria for adverse events (CTCAE) Version 4.03.

Drug-related adverse events are those assessed by investigator as being possibly related or related to study drug.

Treatment-emergent AEs are defined as those events that 1) occur on or after the first day of study drug, and within 30 days following the last dose of study drug or initiation of subsequent cGVHD therapy; 2) any event with missing onset date and its resolution date is during the treatment phase unless the event was indicated in the CRF that was present

before the first day of study drug; 3) any event that is considered study drug-related regardless of the start date of the event; or 4) any event that is present at baseline but worsens in severity or is subsequently considered drug-related by the investigator.

For each adverse event, the percentage of subjects who experience at least 1 occurrence of the given event will be summarized. In the event a patient experiences repeat episodes of the same AE, then the event with the highest severity grade will be used for purposes of incidence tabulations.

Summaries of AEs include:

- Incidence of AEs and serious adverse events (SAEs) by System Organ Class (SOC) and preferred term
- Incidence of AEs and SAEs by preferred term
- Incidence of drug-related AEs and SAEs

AE leading to study treatment discontinuation for the subjects who discontinued study drug due to AE, AE leading to dose reduction, and AEs leading to death will be summarized.

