6.2 Clinical Laboratory Tests

All laboratory values will be converted to SI units and classified as normal, low, or high based on normal ranges of University of California, San Francisco.

The gradable laboratory parameters will be graded using the NCI CTCAE v4.03. The worst postbaseline toxicity grade will be summarized for hematologic and chemistry parameters.

Shift table will also be used to evaluate creatinine clearance.

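### The worst laboratory grade has no end date, so panels drawn in off-drug Response Follow-up count toward it, unlike the treatment-emergent window used for adverse events

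*SAP*

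**What the plan says.** - **Laboratory rule, SAP 6.2:** "The worst postbaseline toxicity grade will be summarized for hematologic and chemistry parameters". A shift table for creatinine clearance is also planned. Neither has an end date.
- **Meaning of postbaseline, SAP 3.1.3:** "The postbaseline value is defined as a measurement taken after the first dose of study drug".
- **Protocol 10.5:** the shift in selected hematology and chemistry parameters "from baseline to the worst toxicity grade during the study will be tabulated". This is no narrower than the SAP.
- **Off-drug visits, Protocol 8.3.1:** "Subjects who discontinue the study for reasons other than progressive disease will be followed every 12 weeks", until progressive disease. Hematology and serum chemistry are on the procedure list, and Appendix A agrees. The same list includes "Review corticosteroid requirements and any new cGVHD treatment if applicable", so starting a new treatment is recorded at these visits and does not end them.
- **Reasons for stopping, Protocol 9.2:** "Malignancy progression/relapse" is listed separately from cGVHD progression.
- **Adverse event window, SAP 6.1:** events count as treatment-emergent if they occur on or after the first day of drug and "within 30 days following the last dose of study drug or initiation of subsequent cGVHD therapy". Events judged drug-related count whatever their start date.

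**The concern.** A worst-grade table in a single-arm study is normally read as a description of what happened under the study drug. Here it would also draw on values taken months after the last dose. By then a subject may be on a different immunosuppressant or, after malignancy relapse, on chemotherapy, which Protocol 6.3 bars only while ibrutinib is being taken. A Grade 4 neutrophil count at such a visit would become that subject's worst grade.

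There is no comparator arm to reveal the inflation. It is also selective, because it arises only in subjects whose reason for stopping sends them to Response Follow-up. And the same value, if judged unrelated to ibrutinib, would appear in the laboratory table but not in the treatment-emergent adverse event table.

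**Working it through.** The plan states no figure for this summary, so there is none to reproduce. The check compares sections, then counts visits.

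**1. Is there a cut-off anywhere?** SAP 6.2 relies on postbaseline, and SAP 3.1.3 bounds that only at first dose. Protocol 10.5 uses the whole study. The visit windows in SAP 3.2 and 8.1 count from first dose and continue every 12 weeks with no off-drug cut. The limit in SAP 6.1 is written for adverse events only. No section I could read sets a laboratory cut-off. The opening of SAP section 2, before 2.1, was not in the text available, and nothing elsewhere points to a laboratory window there.

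**2. Who contributes off-drug panels?** Subjects who progress have panels at the Progressive Disease and End-of-Treatment visits (Protocol 8.2.1, 8.2.2) and then survival contact only (8.3.2). Subjects who stop for another reason go on to 12-weekly panels (8.3.1). That relapsed subjects take the second route is an inference from 8.3.1 read with 9.2. Protocol 3.1 illustrates the group only with adverse events and investigator decision, though it lists follow-up for recurrence of malignancy among that group's activities.

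**3. Direction.** Let A be the grades up to the proposed cut and B the later ones. The maximum over A and B together is never below the maximum over A. Later panels can therefore raise a subject's worst grade but never lower it.

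**4. How many extra panels for a Week 13 stop?** Week 13 has target day 85 (SAP 8.1). On timing after the last dose, Protocol 8.2.2 says "An End-of-Treatment visit should occur 30 days" (± 7 days).
- End-of-Treatment: 85 + 30 = day 115
- First follow-up: 115 + 84 = day 199
- Second: 199 + 84 = day 283
- Third: 283 + 84 = day 367, just past one year

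That gives about two panels within the first year, with a third at the margin. The primary analysis is about 12 months after the last subject's first dose (Protocol 10). Subjects enrolled earlier have longer follow-up, and each further 84 days without cGVHD progression adds about one panel.

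**5. What could that do to one subject?** This is an illustration on assumed inputs. Let p be the chance that a panel shows grade 3 or higher, the same at every panel and independent between panels. A Week 13 stop has six panels through End-of-Treatment: Weeks 2, 5, 9 and 13, the discontinuation visit and End-of-Treatment. With m later panels, the added chance of a worst grade of 3 or higher is (1−p)^6 × [1−(1−p)^m].
- m = 2, p = 1%: 0.9415 × 0.0199 = 1.9 percentage points
- m = 2, p = 10%: 0.5314 × 0.1900 = 10.1 points
- m = 3, p = 1%: 0.9415 × 0.0297 = 2.8 points
- m = 3, p = 10%: 0.5314 × 0.2710 = 14.4 points

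**6. And to the whole table?** The added count is N × f × q, where f is the share entering Response Follow-up and q is the share of those whose first grade 3 or higher value occurs there. The documents give neither f nor q. With N = 40, assumed values of f = 10%, q = 3% give 40 × 0.10 × 0.03 = 0.12 subjects, and f = 40%, q = 20% give 40 × 0.40 × 0.20 = 3.2 subjects. A range this wide shows that the size is set by the assumptions.

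**The case against.** The best defense is that the plan means what it says. Both documents describe a whole-study summary, so they do not contradict each other. The table is descriptive, Protocol 10.5 plans no formal safety testing, and dose-limiting toxicities have their own 28-day window. Clinically significant laboratory abnormalities are recorded as adverse events until 30 days after the last dose (Protocol 7.1.6), so an exposure-limited and attributed account already exists. Late values can also be informative.

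Most of this stands, and it keeps the point modest. It does not explain why one safety table stops near the end of exposure and the other does not.

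Four stronger readings are tempting but not supported:
- *That the SAP labels these values as toxicity on ibrutinib.* It calls them postbaseline. The risk lies in how a single-arm toxicity table will be read.
- *That adverse events have a plain 30-day limit.* SAP 6.1 also closes at subsequent cGVHD therapy, and it stays open for drug-related events. A laboratory cut at 30 days alone would not match it.
- *That vital signs share the problem.* SAP 6.3 summarizes them over time, with no worst value, so the one-way argument does not apply.
- *That the inflation can be put as a percentage of subjects.* Any such figure would rest wholly on assumed shares.

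The creatinine-clearance shift table is a partial case. SAP 6.2 does not say that the shift is to the worst value, so it has the open end but not necessarily the one-way effect.

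**Conclusion.** The point holds on the text: applied literally, the worst-grade rule admits off-drug laboratory values. The effect is upward only and, through Response Follow-up, confined to subjects who stopped without cGVHD progression. It leaves the laboratory and treatment-emergent adverse event tables describing different periods. The only size the documents support is a visit count of about two extra panels in the first year for a Week 13 stop, assuming visits fall on their target days, and more for subjects followed longer. The number of subjects whose worst grade would change cannot be derived and could be below one. No efficacy endpoint, dose decision or formal test depends on it. It is a cheap correction that should be made before the tables are programmed.

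**What to change.** Add one sentence to SAP 6.2: the worst-grade summaries and the creatinine-clearance shift table use values after first dose through 30 days after last dose, or the start of subsequent cGVHD therapy, whichever is earlier. Allow the End-of-Treatment visit's +7 days (Protocol 8.2.2 and Appendix A; Protocol 3.1 gives ± 3 days, so name the window that applies). State which postbaseline value the creatinine-clearance shift uses. List later laboratory values separately.

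The cost is the sentence and a date filter in programming, using dates already collected. The downside is that late values, including any delayed drug effect, appear only in the listing. Reported worst grades stay the same or fall. SAP 6.3 on vital signs needs no change on this account.

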8.1 Visit Window for Analysis

Details for target date for each scheduled visit and time interval between scheduled visits are provided in the table below:

Visit	Start Day	Target Day	End Day
Baseline	Last measurement prior to or on the first dose date		
Cycle Visits			
Week 5	2	29	43
Week 13	44	85	127
Week 25	128	169	211
Week 37	212	253	295
Week 49	296	337	379
Week 61	380	421	463
Week 73	464	505	547
Week 85	548	589	631
Week 97	632	673	715
Week x (every 12 weeks, where $x \geq 97$)	$(x-1)*7-40$	$(x-1)*7+1$	$(x-1)*7+43$

8.2 SAS code to calculate Lee cGVHD symptom scale

This code is copied from the website of Stephanie Lee Lab (<http://research.fhrc.org/lee/en/research-resources.html>)

```

data newdata;
  set olddata;
  *****
  *** Lee chronic GVHD symptom scales ***
  *****
  array oldsx{30} sx1-sx30;
  array newsx{30} b3a b3b b3c b3d b3e b3f b3g b3h b3i b3j b3k b3l b3m
                 b3n b3o b3p b3q b3r b3s b3t b3u b3v b3w b3x b3y b3z
                 b3aa b3bb b3cc b3dd;
  do i = 1 to 30;
    newsx{i}=oldsx{i};
    if newsx{i} not in (0,1,2,3,4) then newsx{i}=. ;
  end;
  if nmiss(b3a,b3b,b3c,b3d,b3e) le 2 then sx_skin=mean(b3a,b3b,b3c,b3d,b3e) *25;
  if nmiss(b3n,b3u,b3v,b3w,b3x,b3y,b3z) le 3 then
    sx_energy=mean(b3n,b3u,b3v,b3w,b3x,b3y,b3z) *25;
  if nmiss(b3l,b3m,b3o,b3p,b3aa) le 2 then
    sx_lung=mean(b3l,b3m,b3o,b3p,b3aa) *25;
  if nmiss(b3f,b3g,b3h) le 1 then sx_eye=mean(b3f,b3g,b3h) *25;
  if nmiss(b3k,b3q,b3r,b3s,b3t) le 2 then
    sx_nutrition=mean(b3k,b3q,b3r,b3s,b3t) *25;
  if nmiss(b3i,b3j) le 1 then sx_mouth=mean(b3i,b3j) *25;
  if nmiss(b3bb,b3cc,b3dd) le 1 then sx_psych=mean(b3bb,b3cc,b3dd) *25;
  if nmiss(sx_skin,sx_energy,sx_lung,sx_eye,sx_nutrition,sx_mouth,sx_psych) le 3

```

```
    then sx_sum =
      mean(sx_skin,sx_energy,sx_lung,sx_eye,sx_nutrition,sx_mouth,sx_psych);
label
  sx_skin = "Lee symptom skin scale (0-100)"
  sx_energy = "Lee symptom energy scale (0-100)"
  sx_lung = "Lee symptom lung scale (0-100)"
  sx_eye = "Lee symptom eye scale (0-100)"
  sx_nutrition = "Lee symptom nutrition scale (0-100)"
  sx_psych = "Lee symptom psychological scale (0-100)"
  sx_mouth = "Lee symptom mouth scale (0-100)"
  sx_sum = "Lee symptom overall summary scale (0-100)";
drop i
  b3a b3b b3c b3d b3e b3f b3g b3h b3i b3j b3k b3l b3m b3n b3o
  b3p b3q b3r b3s b3t b3u b3v b3w b3x b3y b3z b3aa b3bb b3cc b3dd;
run;

proc print data=newdata noobs;
run;
```
